### **2.3.1 Time Point Response**

It is assumed that at each protocol specified time point, a response assessment occurs. [Table A-1](#) on the next page provides a summary of the overall response status calculation at each time point for patients who have measurable disease at baseline.

### **2.3.2 Missing Assessments and Inevaluable Designation**

When no imaging/measurement is done at all at a particular time point, the patient is not evaluable (NE) at that time point. If only a subset of lesion measurements is made at an assessment, usually the case is also considered NE at that time point, unless a convincing argument can be made that the contribution of the individual missing lesion(s) would not change the assigned time point response. This would be most likely to happen in the case of PD. For example, if a patient had a baseline sum of 50 mm with three measured lesions and at follow-up

only two lesions were assessed, but those gave a sum of 80 mm, the patient will have achieved PD status, regardless of the contribution of the missing lesion.

### 2.3.3 Best Overall Response: All Time Points

The *best overall response* is determined once all the data for the patient is known.

**Table A-1 Time point response: patients with target (+/- non-target) disease**

Target lesions	Non-target lesions	New lesions	Overall response
CR	CR	No	CR
CR	Non-CR/non-PD	No	PR
CR	Not evaluated	No	PR
PR	Non-PD or not all evaluated	No	PR
SD	Non-PD or not all evaluated	No	SD
Not all evaluated	Non-PD	No	NE
PD	Any	Yes or No	PD
Any	PD	Yes or No	PD
Any	Any	Yes	PD

CR = complete response, PR = partial response, SD = stable disease, PD = progressive disease, and NE = inevaluable.

*Best response determination in trials where confirmation of complete or partial response IS required:* Complete or partial responses may be claimed only if the objective response is confirmed on a follow-up scan obtained no less than 4 weeks after the initial scan demonstrating an objective response. In this circumstance, the best overall response can be interpreted as in [Table A-2](#).

**Table A-2 Best overall response when confirmation of CR and PR required**

Overall response First time point	Overall response Subsequent time point	BEST overall response
CR	CR	CR
CR	PR	SD, PD or PR a
CR	SD	SD
CR	PD	SD
CR	NE	SD
PR	CR	PR
PR	PR	PR
PR	SD	SD
PR	PD	SD provided minimum criteria for SD duration met, otherwise, PD
PR	NE	SD provided minimum criteria for SD duration met, otherwise, NE
NE	NE	NE

CR = complete response, PR = partial response, SD = stable disease, PD = progressive disease, and NE = inevaluable.

If a CR is *truly* met at first time point, then any disease seen at a subsequent time point, even disease meeting PR criteria relative to baseline, makes the disease PD at that point (since disease must have reappeared after CR). Best response would depend on whether minimum duration for SD was met. However, sometimes ‘CR’ may be claimed when subsequent scans suggest small lesions were likely still present and in fact the patient had PR, not CR at the first time point. Under these circumstances, the original CR should be changed to PR and the best response is PR.

**Special notes on response assessment**

When nodal disease is included in the sum of target lesions and the nodes decrease to ‘normal’ size (< 10 mm), they may still have a measurement reported on scans. This measurement should be recorded even though the nodes are normal in order not to overstate progression should it be based on increase in size of the nodes. As noted earlier, this means that patients with CR may not have a total sum of ‘zero’ on the case report form (CRF).

Patients with a global deterioration of health status requiring discontinuation of treatment without objective evidence of disease progression at that time should be reported as ‘symptomatic deterioration’. Every effort should be made to document objective progression even after discontinuation of treatment. Symptomatic deterioration is *not* a descriptor of an objective response: it is a reason for stopping study therapy. The objective response status of such patients is to be determined by evaluation of target and non-target disease as shown in [Table A-1](#) and [Table A-2](#).

For equivocal findings of progression (e.g., very small and uncertain new lesions; cystic changes or necrosis in existing lesions), treatment may continue until the next scheduled assessment. If at the next scheduled assessment, progression is confirmed, the date of progression should be the earlier date when progression was suspected.

## **2.4 Confirmation/Duration of response**

### **2.4.1 Confirmation**

Objective responses should be confirmed by CT and/or MRI scans obtained no less than 4 weeks after the original scan.

### **2.4.2 Duration of overall response**

The duration of overall response is measured from the time measurement criteria are first met for CR/PR (whichever is first recorded) until the first date that recurrent or progressive disease is objectively documented (taking as reference for progressive disease the smallest measurements recorded on study). The duration of overall complete response is measured from the time measurement criteria are first met for CR until the first date that recurrent disease is objectively documented.

### **2.4.3 Duration of Stable Disease**

Stable disease is measured from the start of the treatment until the criteria for progression are met, taking as reference the *smallest sum on study* (if the baseline sum is the smallest, this is the reference for calculation of PD).

## Appendix 6 Immune-Related RECIST Guidelines

The immune-related RECIST (irRECIST) are adapted from Wolchok 2009 (49).

All patients will be required to have at least 1 measurable lesion to be considered as having measurable disease at baseline for the determination of eligibility for this study. Measurable lesions are defined below.

### 1 Measurability of Tumor at Baseline

#### 1.1 DEFINITIONS

At baseline, tumor lesions/lymph nodes will be categorized measurable or non-measurable as follows:

##### 1.1.1 Measurable

*Tumor lesions:* Must be accurately measured in at least one dimension (*longest* diameter in the plane of measurement is to be recorded) with a *minimum* size of:

- 10 mm by CT scan (CT scan slice thickness no greater than 5 mm).
- 10 mm caliper measurement by clinical exam (lesions which cannot be accurately measured with calipers should be recorded as non-measurable).
- 20 mm by chest X-ray.

*Malignant lymph nodes:* To be considered pathologically enlarged and measurable, a lymph node must be  $\geq 15$  mm in *short* axis when assessed by CT scan (CT scan slice thickness no greater than 5 mm). At baseline and in follow-up, only the *short* axis will be measured and followed. See also notes below on 'Baseline documentation of target and non-target lesions' for information on lymph node measurement.

##### 1.1.2 Non-measurable

All other lesions, including small lesions (longest diameter  $< 10$  mm or pathological lymph nodes with  $\geq 10$  to  $< 15$  mm short axis) as well as truly non-measurable lesions. Lesions considered truly non-measurable include leptomeningeal disease, ascites, pleural or pericardial effusion, inflammatory breast disease, lymphangitic involvement of skin or lung, abdominal masses/abdominal organomegaly identified by physical exam that is not measurable by reproducible imaging techniques.

### **1.1.3 Special Considerations Regarding Lesion Measurability**

Bone lesions, cystic lesions, and lesions previously treated with local therapy require particular comment:

Bone lesions:

- Bone scan, PET scan or plain films are not considered adequate imaging techniques to measure bone lesions. However, these techniques can be used to confirm the presence or disappearance of bone lesions.
- Lytic bone lesions or mixed lytic-blastic lesions, with identifiable soft tissue components, that can be evaluated by cross sectional imaging techniques such as CT or MRI can be considered as measurable lesions if the soft tissue component meets the definition of measurability described above.
- Blastic bone lesions are non-measurable.

Cystic lesions:

- Lesions that meet the criteria for radiographically defined simple cysts should not be considered as malignant lesions (neither measurable nor non-measurable) since they are, by definition, simple cysts.
- ‘Cystic lesions’ thought to represent cystic metastases can be considered as measurable lesions, if they meet the definition of measurability described above. However, if noncystic lesions are present in the same patient, these are preferred for selection as target lesions.

Lesions with prior local treatment:

- Tumor lesions situated in a previously irradiated area, or in an area subjected to other loco-regional therapy, are not considered measurable unless there has been demonstrated progression in the lesion prior to study enrollment.

## **1.2 Specifications by Methods of Measurements**

### **1.2.1 Measurement of Lesions**

All measurements should be recorded in metric notation, using calipers if clinically assessed. All baseline evaluations should be performed as close as possible to the treatment start and never more than 4 weeks before the beginning of the treatment.

## 1.2.2 Method of Assessment

The same method of assessment and the same technique should be used to characterize each identified and reported lesion at baseline and during follow-up. Imaging based evaluation should always be done rather than clinical examination unless the lesions(s) being followed cannot be imaged but are assessable by clinical exam.

*Clinical lesions:* Clinical lesions will only be considered measurable when they are superficial and  $\geq 10$  mm diameter as assessed using calipers (e.g., skin nodules). For the case of skin lesions, documentation by color photography including a ruler to estimate the size of the lesion is suggested. As noted above, when lesions can be evaluated by both clinical exam and imaging, imaging evaluation should be undertaken since it is more objective and may also be reviewed at the end of the study.

*Chest X-ray:* Chest CT is preferred over chest X-ray, particularly when progression is an important endpoint, since CT is more sensitive than X-ray, particularly in identifying new lesions. However, lesions on chest X-ray may be considered measurable if they are clearly defined and surrounded by aerated lung.

*CT, MRI:* CT is the best currently available and reproducible method to measure lesions selected for response assessment. This guideline has defined measurability of lesions on CT scan based on the assumption that CT slice thickness is 5 mm or less. When CT scans have slice thickness greater than 5 mm, the minimum size for a measurable lesion should be twice the slice thickness. MRI is also acceptable in certain situations (e.g., for body scans).

*Ultrasound:* Ultrasound is not useful in assessment of lesion size and should not be used as a method of measurement. Ultrasound examinations cannot be reproduced in their entirety for independent review at a later date and, because they are operator dependent, it cannot be guaranteed that the same technique and measurements will be taken from one assessment to the next. If new lesions are identified by ultrasound in the course of the study, confirmation by CT or MRI is advised. If there is concern about radiation exposure at CT, MRI may be used instead of CT in selected instances.

*Endoscopy, laparoscopy:* The utilization of these techniques for objective tumor evaluation is not advised.

*Tumor markers:* Tumor markers will not be used to assess *objective* tumor response.

## 2 Tumor Response Evaluation

### 2.1 Assessment of Overall Tumor Burden and Measurable Disease

To assess objective response or future progression, it is necessary to estimate the *overall tumor burden at baseline* and use this as a comparator for subsequent measurements. Only patients with measurable disease at baseline should be included. Measurable disease is defined by the presence of at least one measurable lesion (as detailed above).

## 2.2 Baseline Documentation of ‘Target’ And ‘Non-Target’ Lesions

Where more than one measurable lesion is present at baseline all lesions up to a maximum of five lesions total (and a maximum of two lesions per organ) representative of all involved organs should be identified as *target lesions* and will be recorded and measured at baseline. For example, in instances where patients have only one or two organ sites involved, a maximum of two and four lesions respectively will be recorded). Target lesions should be selected on the basis of their size (lesions with the longest diameter), be representative of all involved organs, but in addition should be those that lend themselves to *reproducible repeated measurements*. It may be the case that, on occasion, the largest lesion does not lend itself to reproducible measurement in which circumstance the next largest lesions which can be measured reproducibly should be selected.

*Lymph nodes* merit special mention since they are normal anatomical structures which may be visible by imaging even if not involved by tumor. As noted previously, pathological nodes which are defined as measurable and may be identified as target lesions must meet criterion of a short axis of  $\geq 15$  mm by CT scan. Only the *short* axis of these nodes will contribute to the baseline sum. The short axis of the node is the diameter normally used by radiologists to judge if a node is involved by solid tumor. Nodal size is normally reported as two dimensions in the plane in which the image is obtained (for CT scan this is almost always the axial plane; for MRI the plane of acquisition may be axial, sagittal or coronal). The smaller of these measures is the short axis. For example, an abdominal node which is reported as being 20 mm x30 mm has a short axis of 20 mm and qualifies as a malignant, measurable node. In this example, 20 mm should be recorded as the node measurement. All other pathological nodes (those with short axis  $\geq 10$  mm but  $< 15$  mm) should be considered non-target lesions. Nodes that have a short axis  $< 10$  mm are considered non-pathological and should not be recorded or followed.

A *sum of the diameters* (longest for non-nodal lesions, short axis for nodal lesions) for all target lesions will be calculated and reported as the *baseline sum diameters*. If lymph nodes are to be included in the sum, then as noted above, only the *short* axis is added into the sum. The baseline sum diameters will be used as reference to further characterize any objective tumor regression in the measurable dimension of the disease.

All other lesions (or sites of disease) including pathological lymph nodes should be identified as *non-target lesions* and should also be recorded at baseline. Measurements are not required and these lesions should be followed as ‘present’, ‘absent’, or in rare cases ‘unequivocal progression’. In addition, it is possible to record multiple non-target lesions involving the same organ as a single item on the case record form (e.g., ‘multiple enlarged pelvic lymph nodes’ or ‘multiple liver metastases’).

## 2.3 Response Criteria

This section provides the definitions of the criteria used to determine objective tumor response for target lesions by immune-related response criteria (i.e., irRECIST).

### 2.3.1 Evaluation of Target Lesions

*Immune-Related Complete Response (irCR)*: Disappearance of all target lesions. Any pathological lymph nodes (whether target or non-target) must have reduction in short axis to < 10 mm.

*Immune-Related Partial Response (irPR)*: at least a 30% decrease in the sum of diameters of target lesions, taking as reference the baseline sum diameters.

*Immune-related Progressive Disease (irPD)*: at least a 20% increase in the sum of diameters of target lesions, taking as reference the *smallest sum on study* (this includes the baseline sum if that is the smallest on study). In addition to the relative increase of 20%, the sum must also demonstrate an absolute increase of at least 5 mm.

Unlike conventional RECIST criteria, the appearance of new measurable lesions does not automatically denote disease progression under immune-related response criteria. Rather the dimensions of new measurable lesions are added to overall sum of tumor diameters for determination of objective response status. Patients will not be considered as having progression unless the new overall sum of diameters has increased by  $\geq 20\%$  from the smallest sum of tumor diameters achieved while on study.

*Immune-Related Stable Disease (irSD)*: Neither sufficient shrinkage to qualify for PR nor sufficient increase to qualify for PD, taking as reference the smallest sum diameters while on study.

### 2.3.2 Special Notes on the Assessment of Target Lesions

*Lymph nodes*. Lymph nodes identified as target lesions should always have the actual short axis measurement recorded (measured in the same anatomical plane as the baseline examination), even if the nodes regress to below 10 mm on study. This means that when lymph nodes are included as target lesions, the ‘sum’ of lesions may not be zero even if complete response criteria are met, since a normal lymph node is defined as having a short axis of < 10 mm. In order to qualify for irCR, each node must achieve a short axis < 10 mm. For irPR, irSD and irPD, the actual short axis measurement of the nodes is to be included in the sum of target lesions.

*Target lesions that become ‘too small to measure*. While on study, all lesions (nodal and non-nodal) recorded at baseline should have their actual measurements recorded at each subsequent evaluation, even when very small (e.g., 2 mm). However, sometimes lesions or lymph nodes which are recorded as target lesions at baseline become so faint on CT scan that the radiologist may not feel comfortable assigning an exact measure and may report them as being ‘too small to measure’. When this occurs, it is important that a value be recorded on the case report form. If it is the opinion of the radiologist that the lesion has likely disappeared, the measurement should be recorded as 0 mm. If the lesion is believed to be present and is faintly seen but too small to measure, a default value of 5 mm should be assigned (*Note*: It is less likely that this rule will be used for lymph nodes since they usually have a definable size when normal and are frequently surrounded by fat such as in the retroperitoneum; however, if a lymph node is believed to be

present and is faintly seen but too small to measure, a default value of 5 mm should be assigned in this circumstance as well). This default value is derived from the 5 mm CT slice thickness (but should not be changed with varying CT slice thickness). The measurement of these lesions is potentially non-reproducible, therefore providing this default value will prevent false responses or progressions based upon measurement error. However, if the radiologist is able to provide an actual measure, that should be recorded, even if it is below 5 mm.

*Lesions that split or coalesce on treatment.* When non-nodal lesions ‘fragment’, the longest diameters of the fragmented portions should be added together to calculate the target lesion sum. Similarly, as lesions coalesce, a plane between them may be maintained that would aid in obtaining maximal diameter measurements of each individual lesions. If the lesions have truly coalesced such that they are no longer separable, the vector of the longest diameter in this instance should be the maximal longest diameter for the ‘coalesced lesion’.

### **2.3.3 Evaluation of Non-target Lesions**

This section provides the definitions of the criteria used to determine the tumor response for the group of non-target lesions. While some non-target lesions may actually be measureable, they need not be measured and instead should be assessed only *qualitatively* at the time points specified in the protocol.

*Immune-Related Complete Response (irCR):* Disappearance of all non-target lesions. All lymph nodes must be non-pathological in size (< 10 mm short axis).

*Non-CR/Non-PD:* Persistence of one or more non-target lesions(s)

*Immune-Related Progressive Disease (irPD):* Unlike conventional RECIST 1.1, new measurable lesions or increases in the size of non-target lesions do not define PD in isolation in the immune-related response criteria. Rather, immune-related PD is established if the sum of diameters is  $\geq$  20% of the nadir of the sum of diameters for a given patient.

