### **2.3.4 New Lesions**

The appearance of new malignant lesions alone does not denote disease progression. Instead, the diameter of new lesions is added to the sum of diameters for target and non-target lesions.

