**Immune-related response determination per irRECIST**

Target Lesions	Non-Target Lesions	%Change Tumor Burden	Immune-Related Response Status
CR	CR	-100%	irCR
PR	Any	≤-30%	irPR
PR	Any	≥-30% to <+20%	irSD
PR	Any	≥+20%	irPD
SD	Any	≥-30% to <+20%	irSD
SD	Any	≥+20%	irPD
PD	Any	≥+20%	irPD

No new lesions allowed to achieve irCR status. Otherwise, presence or absence of new measurable or new non-measurable lesions does not affect response status in isolation. New measurable lesions added to cumulative tumor burden to calculate % change tumor burden for the determination of immune-related response status.

**Immune-Related Complete Response (irCR):** Complete disappearance of all target and non-target lesions and no new lesions. The short axis of all lymph nodes must be ≤ 10 mm.

**Immune-Related Partial Response (irPR):** The sum of diameters has decreased ≥ 30% from the baseline but does not meet the criteria for irCR.

**Immune-Related Stable Disease (irSD):** The patient does not meet criteria for irCR, irPR or irPD.

**Immune-Related Progressive Disease (irPD):** The sum of diameters for target lesions and new measureable lesions has increased by ≥ 20% from the nadir sum of diameters.

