## **2.4.4 Special Notes on Response Assessment**

When nodal disease is included in the sum of target lesions and the nodes decrease to ‘normal’ size (< 10 mm), they may still have a measurement reported on scans. This measurement should be recorded even though the nodes are normal in order not to overstate progression should it be based on increase in size of the nodes. As noted earlier, this means that patients with irCR may not have a total sum of ‘zero’ on the case report form (CRF).

Patients with a global deterioration of health status requiring discontinuation of treatment without objective evidence of disease progression at that time should be reported as ‘symptomatic deterioration’. Every effort should be made to document objective progression even after discontinuation of treatment. Symptomatic deterioration is *not* a descriptor of an objective response: it is a reason for stopping study therapy. The objective response status of such patients is to be determined by evaluation of target and non-target disease as shown in Table 1.

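### Protocol Appendix 6 states immune-related progression (irPD) in conflicting ways, leaving the irSD/irPD boundary, and so irRECIST disease control and 16-week irPFS, ambiguous

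*Protocol*

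**What the plan says.** The expansion primary objective (Protocol Section 3.2.1; SAP Section 2.2.1) is measured by objective response rate, disease control rate and the 16-week PFS rate, each under RECIST 1.1 and irRECIST. The irRECIST rules are in Protocol Appendix 6. SAP Sections 5.1.1, 5.1.2 and 6.6.2.1 rely on irRECIST without restating it.

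On how much growth makes irPD, Appendix 6 says:

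- **Section 2.3.1, first rule:** at least a "20% increase in the sum of diameters of target lesions, taking as reference the" smallest value on study, and "the sum must also demonstrate an absolute increase of at least 5 mm".
- **Section 2.3.1, new-lesion paragraph:** "Patients will not be considered as having progression unless the new overall sum of diameters has increased by" 20% or more from the smallest sum. The 5 mm condition is not repeated.
- **Section 2.3.3:** a sum at or above "20% of the nadir of the sum of diameters for a given patient".
- **Section 2.4.1, definitions under the table:** "The sum of diameters for target lesions and new measureable lesions has increased by" 20% or more from the nadir. Neither these definitions nor the table mentions 5 mm.

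On which lesions enter the sum:

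- **Section 2.3.4:** "the diameter of new lesions is added to the sum of diameters for target and non-target lesions".
- **Section 2.2, on non-target lesions:** "Measurements are not required and these lesions should be followed as" present, absent or, rarely, clearly progressing. Section 2.3.3 likewise has them assessed only qualitatively.
- **Sections 2.3.1 and 2.4.1:** target lesions plus new measurable lesions.

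**The concern.** irPD is the threshold that separates a patient counted in irRECIST disease control from one who is not, and it triggers the irPFS event. If a reader at one site applies Section 2.3.1 and another applies the Section 2.4.1 table, the same pair of scans can be irSD for one and irPD for the other. A programmer deriving response from lesion measurements has the same choice, and the SAP does not settle it.

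The same call also bears on conduct. Protocol Section 11.1.1 lets irRECIST prevail for patient management, and Section 5.4 lists irPD among the reasons to stop treatment. The inconsistency can therefore change how long a patient is treated as well as how the scan is tabulated.

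**Working it through.** The plan gives no figure to reproduce on this point, so each rule is applied as written. Let N be the nadir sum and S the current sum, in mm.

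**Rules**

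- Section 2.3.3, literal: S ≥ 0.20 × N
- Section 2.3.1, first rule: S ≥ 1.20 × N and S − N ≥ 5
- Section 2.4.1: S ≥ 1.20 × N

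**Section 2.3.3 read literally**

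Take N = 100 as the smallest earlier sum, so the threshold is 0.20 × 100 = 20.

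| S | Section 2.3.3, literal | Section 2.4.1 |
|---|---|---|
| 100 (unchanged) | irPD | not irPD |
| 70 | irPD | not irPD |
| 20 | irPD | not irPD |
| 19 | not irPD | not irPD |
| 119 | irPD | not irPD |
| 120 | irPD | irPD |

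Only a one-step fall of more than 80% escapes. If the nadir is taken to include the current scan, S can never be below N and every assessment is flagged. Read as an increase of 20% over the nadir, the sentence has the same threshold as Section 2.4.1.

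**Section 2.3.1 against Section 2.4.1**

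A 20% increase is smaller than 5 mm when 0.20 × N < 5, that is, when N < 5/0.20 = 25 mm.

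| N to S (mm) | Increase | Section 2.3.1, first rule | Section 2.4.1 |
|---|---|---|---|
| 15 to 18.5 | 3.5 mm, 3.5/15 = 23.3% | not irPD | irPD |
| 20 to 24 | 4 mm, 20% | not irPD | irPD |
| 24 to 28.8 | 4.8 mm, 20% | not irPD | irPD |
| 25 to 30 | 5 mm, 20% | irPD | irPD |

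Grading the target lesions by Section 2.3.1 first does not remove the conflict. At 15 to 18.5 mm the target status is SD, and the table row for target SD with a burden change of +20% or more still returns irPD.

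Nadirs below 25 mm are possible under the entry rules. One measurable lesion suffices, from 10 mm on CT or 15 mm short axis for a node. A 35 mm sum that shrinks by 30% has a nadir of 35 × 0.70 = 24.5 mm.

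**Which lesions count (assumed example)**

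Target sum 100 growing to 105, with a new measurable lesion of 10 mm: 105 + 10 = 115, or +15%, not irPD under Section 2.4.1. Add a new 8 mm lesion, too small to be measurable, as Section 2.3.4 would allow: 115 + 8 = 123, or +23%, irPD. The further instruction to include non-target diameters cannot be carried out, because those diameters are not recorded.

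**Effect on the endpoints**

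With 25 response-evaluable patients, one patient moved between irSD and irPD changes disease control by 1/25 = 4 percentage points. For best overall response, irPD needs confirmation at least 4 weeks later, so the shift arises when the progression call is confirmed under one rule while the first on-study scan qualifies as irSD under the other. If nobody is censored before week 16, the same patient can move the 16-week irPFS rate by 1/25 = 4 points.

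**irCR items checked for effect**

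The table's irCR row needs −100%, while Section 2.4.4 says "patients with irCR may not have a total sum of" zero. The node limit is ≤ 10 mm in Section 2.4.1 and < 10 mm in Sections 2.3.1 to 2.3.3. A target node starts at 15 mm or more, so at 10 mm it has fallen by at least (15 − 10)/15 = 33.3%. With non-nodal targets gone, a patient who misses irCR on either ground still meets the irPR text. Objective response and disease control count both categories, and irPFS depends on irPD, so none of the three moves.

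**The case against.** A reader might infer that irRECIST response, disease control and irPFS are not defined at all, because one sentence makes nearly every patient progressive. The documents do not support that.

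- Section 2.3.1 (both paragraphs) and Section 2.4.1 all speak of a 20% increase from the smallest or nadir sum, and the table classes a stable tumor as irSD. Section 2.3.3 reads as a slip of wording. This stands. The literal sentence should be corrected, but it is not a rival rule that anyone would apply knowingly.
- A change of exactly −30% appears in both the irPR and irSD rows, but the text settles it. irPR is a decrease of at least 30%, and irSD is what remains. This stands.
- The irCR conflicts move patients only between irCR and irPR. This stands.
- Section 2.3.4 may be loose drafting, since unmeasured lesions have no diameters to add. This stands for existing non-target lesions. It does not dispose of new lesions too small to be measurable, which that section admits to the sum and Section 2.4.1 leaves out.
- Section 2.4.1 may simply omit to repeat the 5 mm condition, and the new-lesion paragraph of Section 2.3.1 gives a necessary condition only. That is a plausible intent, but the table assigns irPD outright and nothing says which text governs.

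It is also fair that the conflict needs a small nadir together with growth of at least 20% but under 5 mm, and that the documents give no distribution of tumor sums. Its frequency is therefore unknown.

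**Conclusion.** The point holds for the irSD/irPD boundary. Two live ambiguities remain once the slip in Section 2.3.3 is set aside: whether 5 mm of growth is required, which matters only for nadir sums below 25 mm, and which new lesions enter the sum. Both feed irRECIST disease control and the 16-week irPFS rate, at up to 4 percentage points per reclassified patient among 25 (for irPFS, assuming no earlier censoring). No expected total shift can be given.

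irRECIST objective response is largely unaffected. irPR is stated consistently in the text, and only the question of which new lesions count could move a sum lying close to the 30% threshold. The RECIST 1.1 versions of the same endpoints rest on Appendix 5 and are not touched. This is a specification defect in one of the two criteria sets behind the expansion primary objective, worth correcting before irRECIST response is derived.

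**What to change.** In Protocol Appendix 6:

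1. Correct Section 2.3.3 to an increase of at least 20% from the nadir, as Sections 2.3.1 and 2.4.1 already have it.
2. Reconcile Sections 2.3.1 and 2.4.1 so that a single statement says whether the 5 mm condition applies, and make the table follow it.
3. Align Section 2.3.4 with Sections 2.3.1 and 2.4.1 on which lesions enter the sum.
4. As minor consistency edits that leave objective response, disease control and irPFS unchanged, align the irCR row with Sections 2.3.2 and 2.4.4 on non-zero nodal sums, use one node limit, and remove the overlap at −30%.

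In SAP Sections 5.1.1 and 5.1.2, cross-reference the single definition. Because irPD also governs whether treatment continues, the choice on the 5 mm condition is the sponsor's, and none is proposed here.

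The cost is appendix wording, an SAP cross-reference and matching programming. No new data are needed.
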